#### **11.3.1.4. Progression-free Survival**

PFS is measured from dose initiation until the first date of objectively documented progression disease or death. Patients who do not have objectively documented progression disease AND not died will be censored at their last documented progression-free date.

#### **11.3.1.5. Overall Survival**

OS is measured from dose initiation until death. Patients who did not die will be censored at their last known alive date.

#### **11.3.1.6. Time to Progression**

TTP is measured from dose initiation until the first date of objectively documented progressive disease. Patients who do not have objectively documented progressive disease will be censored at their last documented progression-free date.

**Note:** Term “objectively documented progressive disease” above refers to PD in the overall response evaluation form.

### **11.3.2. Pharmacokinetic/Pharmacodynamics Analyses**

#### **11.3.2.1. Pharmacokinetic Analyses**

PK analysis will be conducted for Hu5F9-G4 and cetuximab using the PAS. Based on the distinct MOAs of Hu5F9-G4 and cetuximab, drug-drug PK interactions are not expected. Thus, samples for PK analysis for cetuximab will be biobanked and will be analyzed based on CTSC recommendation.

The PAS consists of all patients who have at least 1 blood sample that provides evaluable PK data. The PAS will be used for summaries of PK concentration data, and PK parameters. Individual patients may be removed from the estimation of particular PK parameters based on the number of available blood samples for them. These patients will be identified at the time of analysis.

The PK parameters to be assessed are presented in [Table 16](#).

**Table 16. Noncompartmental Pharmacokinetic Parameters**

AUC last	The AUC from time zero to the last measurable concentration sampling time (t last ) (mass × time × volume - 1)
AUC inf	The AUC from time zero to infinity (mass × time × volume - 1)
AUC tau	The AUC calculated to the end of a dosing interval (tau) at steady-state (amount × time × volume - 1)
C max	The maximum (peak) observed plasma, blood, serum, or other body fluid drug concentration after single dose administration (mass × volume - 1)
T max	The time to reach maximum (peak) plasma, blood, serum, or other body fluid drug concentration after single dose administration (time)
T 1/2	The elimination half-life associated with the terminal slope ( $\lambda z$ ) of a semi logarithmic concentration-time curve (time). Use qualifier for other half-lives
CL	The total body clearance of drug from the plasma (volume × time - 1)
V z	The apparent volume of distribution during terminal phase (associated with $\lambda z$ ) (volume)

PAS will be used in all PK data analysis and PK summary statistics, except for the dose-exposure analysis for Phase 1b.

### **Pharmacokinetic Variables**

The following parameters will be determined by profile using non-compartmental method(s) for Hu5F9-G4:

- AUCinf
- AUC0-168h
- Cmax
- Tmax
- T1/2
- CL
- Vz

Biofluid concentrations will be expressed in mass per volume units. All concentrations below the limit of quantitation or missing data will be reported as such in the concentration data listings. Concentrations below the limit of quantitation will be treated as zero in summary statistics.

Descriptive statistics of all PK parameters will include arithmetic and geometric mean, median, SD, CV, geometric CV, minimum and maximum. Zero

concentrations will not be included in the geometric mean calculation. Since  $T_{max}$  is generally evaluated by a nonparametric method, median values and ranges will be provided for this parameter.

Summary statistics will be presented for Hu5F9-G4 serum concentrations at each scheduled time point. Descriptive graphical plots of individual serum concentration-versus-time profiles and mean concentration-versus-time profiles will be generated.

Missing concentration values will be reported as is in data listings. Concentration values below lower limit of quantitation will be handled as zero in summary statistics, and reported as is in data listings. Any missing PK parameter data will not be imputed.

#### **11.3.2.2. Dose Proportionality**

The analysis of dose proportionality will be conducted for the AUC and  $C_{max}$  of Hu5F9-G4 using a power model on log-transformed scale. The log-transformed PK parameters will each be regressed onto a fixed factor for log (dose). The 90% confidence interval (CI) of the slope for each PK parameter will be computed from the model and presented in a summary table.

#### **11.3.2.3. Immunogenicity Analyses**

The rate and magnitude of anti-Hu5F9-G4 antibody positivity will be evaluated for individual patients, for all patients in the Phase 1b and 2 parts of the trial, and for the pooled patient population. PPD

Immunogenicity analysis will also be performed for cetuximab. However, it is not expected that Hu5F9-G4 will impact the immunogenicity of cetuximab and vice versa.

### **Immunogenicity: Exposure and/or Adverse Event Relationship**

The concentration-versus-adverse event/immunogenicity relationship will be explored graphically, tabulated and, if appropriate, evaluated by a mixed effects model in order to characterize a relationship between the changes from screening immunogenicity presence and serum concentration of Hu5F9-G4.

In addition, the potential correlation between immunogenicity and other endpoints (major safety, efficacy, and biomarker parameters) may be evaluated. This will be done in 2 steps. First, a descriptive analysis will be performed graphically between immunogenicity change from screening values and major safety, efficacy, and biomarker parameters (either as categories or continuous variables). Second, for any potential correlation identified, further investigation will be performed using a mechanism-based modeling approach, as appropriate.

#### **11.3.2.4. Pharmacodynamic and Biomarker Analyses**

PPD

#### **11.3.3. Safety Analyses**

The statistical analysis of safety will be conducted for patients in the SAF. The statistical analysis will be descriptive, providing listings, graphical displays, frequencies, and percentages for discrete variables and/or the mean, standard deviation, median, and ranges for continuous variables. Safety variables to be examined include DLTs, treatment-emergent adverse events (TEAEs: AEs worsening or occurring during or after a patient's first exposure to study drugs), vital signs, physical examinations, laboratory, receptor occupancy, and antidrug antibody assessments. Adverse events will be coded using Medical Dictionary for Regulatory Activities (MedDRA, Version 17.1 or later) and grouped by system organ class and preferred term.

Data will be presented by Phase 1b dose cohort and Phase 2 arm, where relevant, summarized across various dose cohorts. Data may be graphed, summarized, or listed depending on the amount of data to be reported. Where relevant, safety data will also be presented by the study day/study day interval corresponding to dose administrations within each dose cohort.

#### **11.3.3.1. Adverse Events**

For the safety Analysis Set, AEs that occurred during Screening, but before exposure to study drugs will be reported in the AE line listings and appropriately identified as non-TEAEs. Summary tables of TEAEs will be provided using the NCI CTCAE Version 4.03 to describe the type and severity of event. Peripheral smear assessments will be tabulated and reported separately. TEAEs will also be tabulated using Investigator assessment of the relationship to study drugs (related or not related). SAEs, including deaths, will be summarized and/or listed for each dose cohort and for all dose cohorts combined. TEAEs resulting in withdrawal from study drugs or further study participation will be tabulated and/or listed. DLTs will also be listed. Unless otherwise noted, the tabulation of AEs will be based on patient incidence rather than event incidence.

Adverse events and SAEs occurring during Screening will be reported separately for patients in the Screened-only Set with line listings and/or summary tables, along with relevant demographic data collected.

#### **11.3.3.2. Analysis of Other Safety Endpoints**

The analysis of other safety endpoints such as vital signs, peripheral smear assessments, and other laboratory assessments, will include listings, graphical displays, and descriptive statistics such as change from baseline and/or shift tables, where relevant. Details will be provided in the SAP.

### **11.4. Interim Analysis**

An interim analysis would be conducted on the first 15 efficacy evaluable patients for each cohort in Phase 2. If median PFS is no more than 2 months and objective

response rate is less than 10%, then there would be no further enrollment into the cohort. CTSC would decide whether or not to further expand a cohort based on the totality of the efficacy as well as safety data.

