## **11.2. Sample Size Determination**

The total number of patients in this trial will include as many as 112 patients. This sample size includes the Phase 1b and Phase 2 parts of the study. In Phase 1b, a standard 3+3 dose escalation design will be used to explore the MTD of the investigational study drug combination in patients with solid tumors. An estimated 32 patients will be enrolled in Phase 1b, depending on dose escalation and expansion.

Phase 2 includes 2 arms, one comprising patients with KRAS mutant CRC and the other comprising patients with KRAS wild-type CRC, in which enrollment in one or both arms may be modified based on emerging data. A total of 88 patients (44 patients per arm) will be enrolled in Phase 2, assuming progression to Stage 2 for both arms. This sample size estimate was determined using a one-sided alpha level of 0.10 and a power of 0.80 based on a null hypothesis of 5% response rate compared to an alternative hypothesis of 15% for each cohort.

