## **11.3. Statistical Methods**

All analyses will be descriptive in nature. Descriptive statistics will be provided for all safety and efficacy endpoints.

All analyses will be conducted separately for patients in Phase 1b and Phase 2 parts of the study. However, safety analyses may be conducted for patients in both Phase 1b and Phase 2. In addition, efficacy analyses will be conducted separately for the two cohorts in Phase 2.

For continuous variables, the mean, standard deviation, median, and ranges will be provided. For categorical variables, the frequency and percentage in each category will be provided along with confidence intervals for primary and secondary efficacy endpoints. For time-to-event variables, the Kaplan-Meier (KM) estimates and corresponding two-sided 95% confidence intervals for the median and quartiles will be provided. The KM plot may also be provided. Details regarding the statistical

analysis to be conducted, including the handling of missing data and patient withdrawal, will be provided in the SAP.

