1.3 Sample Size Determination

Depending on dose escalation and expansion, an estimated number of 15 to 24 patients will be enrolled in Phase 1b, and 88 patients will be enrolled in Phase 2.

No formal hypothesis testing will be done. In Phase 2, it is planned to enroll an expansion cohort of 44 patients with KRAS mutant CRC and another expansion cohort of 44 patients with KRAS wild-type CRC. This sample size was determined using a one-sided alpha level of 0.10 and a power of 80% based on a null hypothesis of 5% response rate compared with an alternative hypothesis of 15% for each cohort.

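### The 80% power behind 44 patients per Phase 2 cohort is not secured once the futility rule at 15 patients is followed; it then lies between 0.62 and 0.81, depending on an unstated PFS assumption

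*Protocol*

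**What the plan says.** **Sample size.** Protocol 11.2 sets 44 patients per Phase 2 arm, 88 in total, "assuming progression to Stage 2 for both arms". The basis is a 5% null against a 15% alternative response rate in each cohort: "This sample size estimate was determined using a one-sided alpha level of 0.10 and a power of 0.80". SAP 1.3 repeats the same inputs. Neither section names the design, gives a number of responses that counts as success, or refers to an interim look.

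**Interim rule.** Protocol 11.4 places a look at the first 15 efficacy-evaluable patients in each cohort. The rule has two conditions, both needed. It opens with the PFS condition, "If median PFS is no more than 2 months and objective", and then turns to the response condition and what follows from it: "response rate is less than 10%, then there would be no further enrollment into the cohort". The next sentence says "CTSC would decide whether or not to further expand a cohort based on the totality of the efficacy as well as safety data".

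**Status in the SAP.** SAP 1.1 keeps the enrollment hold and the interim analysis at 15 per cohort but gives no criteria. SAP 7, which lists departures from the protocol's analyses, does not mention the rule. Protocol 11.4 is therefore its only source, and it still applies.

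**Status of testing.** Protocol 11.3 says "All analyses will be descriptive in nature", and SAP 1.3 says "No formal hypothesis testing will be done".

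**The concern.** Power is the only reason given for 44 per cohort. A reader will take 80% as the chance that a regimen with the targeted 15% response rate ends as a success. A rule that can close a cohort at 15 patients can only lower that chance. With 15 patients, a response rate below 10% means 0 or 1 response (1/15 = 6.7%, 2/15 = 13.3%), which is not rare for a regimen whose true rate is 15%. If the PFS condition is often met as well, a cohort that deserved to continue is lost more often than the sample-size sections suggest.

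**Working it through.** **Inputs.** Null rate 0.05, alternative 0.15, one-sided alpha 0.10, power 0.80, n = 44 (Protocol 11.2, SAP 1.3). Look at 15, stop if 0–1 responses and median PFS ≤ 2 months (Protocol 11.4). All probabilities are exact binomial.

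**1. Reproduce 44.** Because no success cut is stated, take the smallest cut that respects alpha 0.10.

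| Success cut, n = 44 | Alpha (5%) | Power (15%) |
|---|---|---|
| ≥ 4 | 0.177 | 0.913 |
| ≥ 5 | 0.067 | 0.810 |
| ≥ 6 | 0.022 | 0.664 |

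The cut is ≥ 5. With 43 patients the same cut gives power 0.793. In an exact search from n = 30 upward, 44 is the first size that meets both targets, so the plan's number is reproduced.

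A single stage is not the only fit. The Stage 2 wording in Protocol 11.2 suggests a two-stage design, and 51 two-stage designs that stop on response alone, with a total of 44, also meet 0.10/0.80. All have a first look at 21 or more patients, success at ≥ 5 and power 0.80–0.81. One example is 29 patients, stopping at ≤ 1 (alpha 0.065, power 0.801).

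**2. How often the response condition is met.** P(0 of 15) + P(1 of 15):
- at 15%: 0.0874 + 0.2312 = 0.319
- at 5%: 0.4633 + 0.3658 = 0.829

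**3. Power at stake.** These cohorts could still have reached 5 of 44 through the other 29 patients. At 15%:
- 0 responders so far: 0.0874 × P(≥ 5 of 29) = 0.0874 × 0.4445 = 0.0388
- 1 responder so far: 0.2312 × P(≥ 4 of 29) = 0.2312 × 0.6513 = 0.1506
- total: 0.1894

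**4. Power with the rule followed.** Let q be the chance that the PFS condition is met given 0–1 responders in 15 (taken as the same for 0 and 1; the two bounds do not depend on this).

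Power = 0.8097 − 0.1894q

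| q | 0 | 0.25 | 0.50 | 0.75 | 1 |
|---|---|---|---|---|---|
| Power | 0.810 | 0.762 | 0.715 | 0.668 | 0.620 |

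Power is at least 0.80 only if q ≤ (0.8097 − 0.80)/0.1894 = 0.051.

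**5. Alpha with the rule followed.** At 5% the same sum is 0.0063 + 0.0200 = 0.0263, so alpha lies between 0.067 and 0.067 − 0.026 = 0.041.

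**6. Sensitivity to the cut.** If the PFS condition were always met and the cut relaxed to ≥ 4 of 44, alpha would be 0.087 and power 0.664, still well below 0.80.

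**7. Why q cannot be read off.** The only PFS figure in the readable text is the 2-month threshold. The first tumor assessment is at Cycle 3 Day 1 ± 1 week (Protocol 7.9), that is 56 ± 7 = 49 to 63 days after the first dose. Two calendar months (2 × 365.25/12 = 60.9 days) and two cycles (56 days) both fall inside that window, so the length of a month can affect whether the PFS condition is met.

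**The case against.** **The rule is joint, so the stated 80% may already allow for it.** This stands in part. A reader might infer that the calculation must have ignored the look at 15, because no design that stops on response alone, with a first stage of 15 and a total of 44, meets 0.10/0.80. That does not follow. The actual rule also needs a short median PFS, and if that is met no more than about 5% of the time, power stays at 0.80 or above. The documents show that the sample-size sections do not mention the rule. They do not prove that the calculation excluded it.

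**A PFS assumption may exist in the design schema.** This also stands. The figure is not shown here, and its abbreviation list includes H0, H1 and PFS. The absence of a PFS assumption can be asserted only for the readable text.

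**The success cut is inferred.** True, and 0.62 is a bound only if ≥ 5 of 44 is kept. Relaxing the cut raises the lower bound only to 0.66.

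**The rule is advisory and nothing is tested.** The steering committee decides on all the data, and Protocol 3.3 lets it open full accrual early. Most of the possible loss (0.151 of 0.189) comes from cohorts with exactly one responder in 15, where that discretion is most likely to be used. This limits the consequence. It does not make the stated 80% right when the rule is followed, and a descriptive trial that quotes power as its reason for 44 should still quote it correctly.

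**Conclusion.** The concern holds in a limited form. The sample size of 44 is sound for the stated inputs without the look at 15. Once the Protocol 11.4 rule is followed, the stated 80% is not secured: single-stage power lies between 0.81 and a lower bound of 0.62, and alpha between 0.067 and 0.041. This rests on the inferred cut of ≥ 5 of 44 and on the rule being followed.

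A reader might take 62% as the true power. The documents do not support that. It is the value if the PFS condition is met every time the response condition is, and nothing in the readable text says how often that would be. If the PFS condition is rarely met, the loss is negligible.

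The practical effect is on how the sample size is described and on what the committee and readers expect of the look at 15. It does not affect any planned test or estimate. It should be corrected because power is the sole justification for 44 and the correction is cheap.

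**What to change.** In Protocol 11.2 and SAP 1.3:
- name the design (single stage, or two-stage with its first-stage size and stopping number) and the success cut;
- restate power and alpha with the rule at 15 patients included, either under a stated PFS assumption with 2 months defined in days, or as a range;
- say that the steering committee may depart from the rule.

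Possible wording, if the design is single stage: *Forty-four patients per cohort (success if at least 5 respond) give 81% power and one-sided alpha 0.067 without the Section 11.4 rule. If that rule is followed, power is between 62% and 81% and alpha between 0.041 and 0.067, depending on how often median PFS is at most 2 months ([x] days). The CTSC may depart from the rule.*

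If the schema figure already carries a PFS assumption, cite it there and give the single resulting power.

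The cost is a few sentences and a less favourable stated power. No extra patients and no change to the rule are needed.

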## **12. ETHICAL AND ADMINISTRATIVE CONSIDERATIONS**

### **12.1. Compliance Statement**

This study will be conducted in accordance with the protocol and with US Food and Drug Administration (FDA) and the International Conference on Harmonisation (ICH) good clinical practice (GCP) guidelines, the Declaration of Helsinki, and any applicable local health authority and Institutional Review Board (IRB)/Independent Ethics Committee (IEC) requirements.

To the extent applicable, all references to the FDA, Federal Food, Drug, and Cosmetic Act, Code of Federal Regulations (CFR), ICH, GCP, and the like shall be interpreted as also referring to any corresponding requirements of local regulatory agencies, regulations, and laws. If there is any discrepancy between FDA, ICH, and local requirements, the most stringent standard shall apply.

### **12.2. Investigator Responsibilities**

As required by FDA regulation (21 CFR Part 56) and ICH guidelines for GCP, the Investigator at each study site must obtain IRB/IEC review and approval of the study protocol, ICFs, patient recruitment materials, and any other pertinent documents before any study-related activities involving patients are performed.

As required in 21 CFR Part 50 and ICH guidelines for GCP, the Investigator or designee must comply with the informed consent process, and ensure that each patient enrolled in this clinical study understands the information presented in the IRB/IEC approved ICF and agrees voluntarily to participate in the clinical study.

The Investigator or designee must submit to the IRB/IEC any written safety report or update (e.g., amended Investigator's Brochure or safety amendments and updates) provided by the Sponsor or representative, according to the IEC specific reporting requirements.

The Investigator must inform the IRB/IEC of the progress of the clinical study and report any non-administrative changes made to the protocol; in any case, the

Investigator must provide an update to the IRB/IEC at least once a year or in accordance with IRB/IEC continuing approval requirements.

The Investigator must maintain a list of appropriately qualified persons to whom he/she has delegated study duties. All persons authorized to make entries and/or corrections on eCRFs or other reporting forms will be included on the Forty Seven Inc. Delegation of Authority Form.

The clinical study report must be signed by the Investigator or, in the case of multi-center studies, the Coordinating Investigator. The Coordinating Investigator, identified by Forty Seven Inc., will be any or all of the following:

- a recognized expert in the therapeutic area.
- an Investigator who provided significant contributions to either the design or interpretation of the study.
- an Investigator contributing a high number of eligible patients.

### **12.3. Institutional Review Board or Independent Ethics Committee**

A copy of the protocol, proposed informed consent form, other written patient information, and any proposed advertising material must be submitted to the IRB/IEC for written approval. A copy of the written approval of the protocol and informed consent form must be received by Forty Seven Inc. before recruitment of patients into the study and shipment of Hu5F9-G4.

The Investigator must submit and, where necessary, obtain approval from the IRB/IEC for all subsequent protocol amendments and changes to the informed consent document. The Investigator is to notify the IRB/IEC of deviations from the protocol or SAEs occurring at the site and other AE reports received from Forty Seven Inc., in accordance with local procedures.

The Investigator is responsible for obtaining annual IRB/IEC approval/renewal as applicable throughout the duration of the study. Copies of the Investigator's reports and the IRB/IEC continuance of approval must be sent to Forty Seven Inc.

#### **12.4. Informed Consent and Human Subject Protection**

An initial sample informed consent form is provided for the Investigator to prepare the informed consent document to be used at his or her site. Updates to the template are to be communicated formally in writing from the Forty Seven Inc. Study Monitor to the Investigator. The written informed consent document is to be prepared in the language(s) of the potential patient population.

Before a patient's participation in the clinical study, the Investigator is responsible for obtaining written informed consent from the patient or legally acceptable representative after adequate explanation of the aims, methods, anticipated benefits, and potential hazards of the study and before any protocol-specific screening procedures or any investigational products are administered. A legally acceptable representative is an individual or other body authorized under applicable law to consent, on behalf of a prospective subject, to the subject's participation in the clinical study.

The Investigator is also responsible for asking the patient if the patient has a primary care physician and if the patient agrees to have his/her primary care physician informed of the patient's participation in the clinical study. If the patient agrees to such notification, the Investigator is to inform the patient's primary care physician of the patient's participation in the clinical study. If the patient does not have a primary care physician and the Investigator will be acting in that capacity, the Investigator is to document such in the patient's medical record. The acquisition of informed consent and the patient's agreement or refusal of his/her notification of the primary care physician is to be documented in the patient's medical records, and the informed consent form is to be signed and personally dated by the patient, or a legally acceptable representative, and by the person who conducted the informed consent discussion. The original signed informed consent form is to be retained in accordance with institutional policy, and a copy of the signed consent form is to be provided to the patient or legally acceptable representative.

If a potential patient is illiterate or visually impaired and does not have a legally acceptable representative, the Investigator must provide an impartial witness to read the informed consent form to the patient and must allow for questions. Thereafter, both the patient and the witness must sign the informed consent form to attest that informed consent was freely given and understood.

